**C. Who will be involved in the process of consent and what are their responsibilities?**

For Aim 1, patients who are interested as identified through clinical trial registry will be contacted by a member of the research team to review participation in the study and determine eligibility criteria and if eligible will complete the informed consent process for the semi-structured focus groups.

In the instance where the participant is identified by any BHP and wishes to participate in the study using the QR code contact information to a member of the research team will be provided to the participant to review any questions they may have pertaining to the consent prior to starting any survey questions.

[name] will be consenting BHP's, Clinical Staff, Providers and Administration

**D. How much time will be allotted to the process of consent?**

The consent process is likely to take between 5-10 minutes. However, more time will be provided if needed. We will follow up with the BHP, Clinical Staff, Providers and Administration's manager to determine BHP, Clinical Staff, Providers and Administration interest and invite those interested in participating to complete the informed consent. BHPs at the participating clinic site will identify patients who meet the eligibility criteria and determine interest in participation.

**E. How will the process of consent be structured for subjects who are likely to be more vulnerable to coercion or undue influence?**

Informed consent will be completed in the office of the BHP or with UNMC research Team member on this IRB approved who is identified via clinical trial registry or during their standard of care appointment. Consent will be completed virtually or in written format for in person visits, as such, it will be read aloud to participants. Participants will have additional time, if needed, for delayed consent and encouraged to discuss their participation with family/friends. Only Citi trained and UNMC IRB approved members of this IRB application will be performing consent.

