## **CHARACTERISTICS OF THE SUBJECT POPULATION**

### **4. Accrual**

**A. Is this study conducted solely at sites under the oversight of the UNMC IRB (e.g. UNMC, Nebraska Medicine, CHMC, UNO)?**

Yes

**1. How many subjects will need to be consented (per group, as applicable) in order to achieve the scientific objectives of the research?**

Aim 1: Total 14 - 10 patients and 4 behavioral health providers

Aim 2: Total 45 - Patients (15), BHPs (10), Clinical staff, providers and administration (20)

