**D. What provisions will be in place to protect the subject's privacy? Check all that apply.**

- ◆ Ensuring that only personnel listed on the IRB application Section I.3(A-E) are present during the consent process.
- ◆ Ensuring that the fewest number of individuals possible are aware of the subject's participation in the research.
- ◆ Ensuring that the research activities are performed in as private of a place as possible.

Other. Explain.

**E. Does this research involve data banking at UNMC, NM, UNO or CHMC, or by an outside organization (e.g. NCI Cooperative Group, pharmaceutical company) for future**

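### Staff interest in taking part is determined through their manager, so up to 30 of the 45 planned Aim 2 participants are approached through a superior, with no staff safeguard in the visible text

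*Combined protocol and SAP*

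**What the plan says.** Section II, item 29.D, which otherwise deals with the time allotted to consent, contains the only description of staff recruitment in the visible text. The study team will follow up with the staff's "manager to determine BHP, Clinical Staff, Providers and Administration interest and invite those interested in participating to complete the informed consent". The sentence covers every staff category and is not limited to one aim.

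Item 4.A.1 gives the planned numbers: "Aim 1: Total 14 - 10 patients and 4 behavioral health providers" for the first aim, and for the second 15 patients, 10 BHPs and 20 clinical staff, providers and administration, 45 in all.

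Other provisions bear on the same people:

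- **Consent (item 29.C).** One study team member "will be consenting BHP's, Clinical Staff, Providers and Administration".
- **Privacy (item 15.D).** Two ticked provisions are "Ensuring that the fewest number of individuals possible are aware of the subject's participation in the research" and "Ensuring that only personnel listed on the IRB application Section I.3(A-E) are present during the consent process".
- **Staff list (item 15.B).** The file linking staff names to study IDs is open to one team member only.
- **Interviews (item 12.B, Focus Group and Semi-Structured Interviews for Aim 2).** The study team interviews staff in private at the clinic or by Zoom, on feasibility, acceptability and usability. Topics include professional interactions, incentives and resources, and the organization's capacity to change.

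**The concern.** Aim 2 is a feasibility pilot, and the staff interviews are a main source of its evidence on implementation. Entry to those interviews passes through a person with authority over the interviewee. Two things could follow. The people put forward may differ from the staff as a whole. Those who take part may also speak less freely about incentives, colleagues or the organization if they think a superior knows they came forward. Either would weaken what the interviews are for, which is finding barriers before a larger trial.

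Nothing in the visible text would let a reader see afterwards whether entry was selective. It plans no count of staff eligible or approached at each clinic.

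There is also a question of internal consistency. The protocol undertakes to keep knowledge of participation to as few people as it can and locks the staff list to one person. Yet it brings in a manager before any of those protections apply.

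**Working it through.** **Step 1. Reproduce the planned total.** From item 4.A.1: 15 patients + 10 BHPs + 20 other staff = 45, which matches the stated Aim 2 total.

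**Step 2. Count those covered by the manager route.** 10 + 20 = 30, and 30 / 45 = 66.7%. This is an upper bound, because the administration group may include the managers themselves.

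**Step 3. Allow for Aim 1.** The sentence in 29.D is not restricted to Aim 2. If the 4 Aim 1 BHPs enter the same way, the count is up to 30 + 4 = 34 of 14 + 45 = 59 planned enrolments, or 57.6%. The same BHP may appear in both aims, so these are enrolments and not necessarily different people.

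**Step 4. Trace who learns what.**

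| Stage | Who acts | Source | What the manager learns |
|---|---|---|---|
| Interest determined | Team, through the manager | 29.D | Possibly who is interested |
| Invitation | Study team | 29.D | Not stated |
| Consent | One team member, listed personnel only | 29.C, 15.D | Not stated |
| Name and ID list | One team member | 15.B | No access |
| Interview | Study team, in private or by Zoom | 12.B | Not stated |

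The exposure is at the first stage. The later protections are real, but they cannot undo what the manager may already know.

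**Step 5. Look for a safeguard at that stage.** Item 29.E, on undue influence, offers extra time and a chance to talk to family or friends, and says nothing of a superior. The item 8 safeguards are written for four ticked groups, none of them staff; the box for employees of the investigator is not ticked. The assurance there that taking part will not harm the relationship with clinic staff is aimed at patients, and no counterpart for employment appears. At Bluestem the site investigator also supervises other BHPs (item 12.B, Aim 2), again with no stated protection for them.

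**Step 6. Can the bias be sized?** No. That would need the number of eligible staff at each clinic, the way the manager determines interest, and how views differ between staff put forward and staff not. None of these is given. Nor is there a planned estimate to correct: the interviews are analyzed by directed content analysis (item 12.E), and the two staff questionnaires, on comfort with apps and on self-management support, go to BHPs only (item 12.D).

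**The case against.** The case on the other side is substantial, and several stronger readings fail against it.

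- **That managers know who takes part.** A reader might infer this, but the text shows only that the manager is consulted about interest. Consent, the name list and the interviews are all with the study team. Knowledge of final participation is plausible but not stated.
- **That managers choose the participants.** The sentence has the team doing the inviting. It would fit a manager who circulates a notice or reports a headcount. Selection by the manager is possible under the wording, not prescribed by it.
- **That the results will be biased toward favourable views.** Neither direction nor size can be shown. A manager might simply name whoever is free. If 30 is close to the whole eligible staff, selection has little room to act.
- **That the privacy provision is contradicted.** Its standard is relative, so the fair word is tension.
- **That the clinics' support for the study (item 33) shows pressure.** It reads as ordinary site permission.

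It is also fair to say that 66.7% is a headcount: staff contribute nothing to the patient symptom models. Parts of the identification and recruitment section and the consent pages were not in the text reviewed, so an assurance to employees could exist there.

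These points limit the claim without removing it. On any reading of 29.D, interest is gauged through a superior when the team could ask staff directly, and the visible text does not say what the manager may learn.

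**Conclusion.** The point holds as a weakness in the recruitment rule. It does not demonstrate bias. Up to 30 of the 45 planned Aim 2 participants (66.7%) are approached through a manager who may learn who is interested. The consequence is a risk, of unknown size and direction, of selective entry and less candid answers in the staff interviews on feasibility and acceptability. The rule is in tension with the undertaking in item 15.D and with the restricted list in item 15.B, and the visible text describes no safeguard specific to employees.

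This rests on three assumptions: that 29.D is the only staff route, that it applies to all 30, and that no employee assurance sits in pages not seen. If managers are among the 20, the count falls. The stakes are modest in a small feasibility pilot, but the remedy is cheap and protects evidence meant to shape a larger trial.

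**What to change.** Replace the sentence in item 29.D with a rule of this kind:

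1. The manager at each clinic gives the research team only a full list of eligible BHPs, clinical staff, providers and administration.
2. The research team invites everyone on the list directly and individually.
3. The research team does not tell managers who is interested or who accepts.
4. The report gives the number invited and the number interviewed, by role.

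The first three parts remove the manager from the interest step and bring 29.D into line with items 15.B and 15.D. The fourth supplies the denominator that readers need to judge selective entry.

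The cost is one rewritten sentence, a standard invitation email and slightly more contact effort by the research team. Sample size, instruments and analysis are unchanged.

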**F. Will non-English speaking subjects be enrolled in this research?**

No

**Provide justification for exclusion of non-English speaking subjects**

Because of limited funding, we will focus on recruiting English speaking subjects only. When we expand the study in the future, we will translate all the materials in Spanish to recruit Spanish-speaking subjects as well.

**G. How will it be determined that the subject/parent(s)/guardian(s)/LAR understood the information presented?**

The participants will be asked about their understanding of the elements of informed consent prior to determining if the information presented was understood. The BHP and designated research staff will use open-ended questions to assess if participants understand what they believe need to do to participate in the study. If they do not communicate understanding, the study and aspects of their potential participation will be described to them again.

**31. Consent Forms and Study Information Sheets**

**Indicate the type of consent forms and study information sheets to be used in this research. Check all that apply.**

♦ Adult consent form

Legally authorized representative (LAR) consent form

Parental/Guardian consent form

Youth study information sheet

Child study information sheet

Adult study information sheet (decisionally-impaired)

Screening consent form

Addendum consent form

Other. Explain.

### **32. Information Purposely Withheld**

**Will any information be purposely withheld from the subject during the research or after completion of the research?**

No

## **RESOURCES**

### **33. Describe the resources available to safely conduct this study at each study sites specified in Section I.7.**

We will use funding from Great Plains IDeA-CTR grant to hire study personnel to help to conduct research activities. Also, the Nebraska Medical Center Clinics approved our request to conduct the study at their sites and are in support of their health care providers participating in and supporting our study. The BHPs at the Nebraska Medicine Clinics and Bluestem Clinics will recruit patients and implement the app intervention. We have received verification of additional support for adding this site from the Director of the Bluestem Health system. Additionally, a member of our research team, [name], provides direct patient care services for Bluestem.

## SECTION III

### SUBMISSION DEADLINE

#### A. Full Board Review:

The IRB meets twice monthly, on the first and third Thursday of the month, with the exception of January and July when the IRB meets only on the third Thursday of the month. No more than 15 applications (e.g., initial review of a new study, re-review of a tabled study) will be reviewed at each meeting. All reviews are performed on a first-come first-served basis. The IRB meeting schedule and deadline dates can be found on the IRB website at [www.unmc.edu/irb](http://www.unmc.edu/irb).

#### B. Expedited Review

Applications that qualify for expedited review have no submission deadline and can be reviewed independent of the IRB meeting schedule. Call the Office of Regulatory Affairs for assistance in determining if your study meets the requirements for expedited review.

### ADDITIONAL REVIEW REQUIREMENTS

Final IRB approval and release of studies is contingent upon approval by the following UNMC committees or departments. Check the appropriate boxes:

**UNMC and NM - Pharmacy & Therapeutics (P&T) Committee** (Required for studies involving drugs)

**Fred & Pamela Buffett Cancer Center Scientific Review Committee (SRC)** (Required for studies involving cancer)

**Institutional Biosafety Committee (IBC)** (Required for studies involving the use of gene transfer and vaccines)

**Investigational Device Review Committee (IDRC)** Review by the IDRC is required for all protocols involving the use of investigational or marketed devices

**Billing Grid** (Required for all studies involving billing for hospital/clinic services)

**Coverage Analysis** (Departments requiring this analysis have been specified by the Organization)

**Conflict of Interest (COI) Management Plan** (Required for all studies with declared COI by study personnel)

**Sponsored Programs Administration (SPA)/UNeHealth** grants and contracts

**Pathology approval** for collection of tissue samples required for this study

**Radiation Committee Approval**

**Other Review**

♦ **None of the above organizational requirements apply to this study**

## SECTION IV

### COVID-19

#### **Human Subjects Research Safety Plan**

**You have indicated in section I that this study involves face to face contact with subjects. Before final approval and release of this study will be issued, a Human Subjects Research Safety Plan found at [unmcrcedcap.unmc.edu/redcap](http://unmcrcedcap.unmc.edu/redcap) must be completed and submitted to the Human Subject Research Safety Review Committee (HSRSRC) for review and approval.**

- ◆ I acknowledge this requirement.

**ADDENDUM B**

**Research Involving Pregnant Women, Fetuses and Neonates of Uncertain  
Viability or Non-Viable**

**Title of Protocol**

Using Mobile Technology to Address the Trauma Mental Health Treatment Gap:  
Developing Implementation Protocols for Primary Care

**1. Preclinical Studies and Studies on Non-Pregnant Women [45 CFR 46.204(A)]**

**A. Will Pregnant women/fetuses be included in the research?**

Yes

**B. Have scientifically appropriate preclinical studies, including studies on pregnant animals, and clinical studies, including studies on non-pregnant women, been conducted?**

No

**C. Do these studies provide data for assessing potential risks to pregnant women and fetuses?**

No

**2. Risks and Benefits to the Pregnant Woman or Fetus which are Associated with the Research [45 CFR 46.204(B)]**

**A. Is there *any* prospect of direct benefit for the woman or the fetus?**

No

**1) Describe any risks to the fetus.**

Pregnant women are not being exclusively targeted for this research but they may be a part of the data and are not being specifically excluded as they may also suffer from mental illnesses. As the study involves the use of mobile apps in addition to surveys and semi-structured interviews for primary data collection, there is no research-based risk to the fetus or the woman herself.

**2) Describe how the research could lead to the development of important biomedical knowledge.**

Our results will directly inform how technology-based strategies may improve trauma-focused care for underserved populations and shape procedures for a larger clinical trial that may be conducted with the fully-developed and refined educational materials and procedures based on analyses from these data.

**3) Could the research be conducted without involvement of pregnant women?**

Yes

**3. Minimization of Risks to the Pregnant Woman and Fetus [45 CFR 46.204(C)]**

**A. Describe how the risks to the pregnant woman and fetus are minimized to the greatest extent possible consistent with the objectives of the research.**

The methods employed for this study with voluntary participation itself minimizes the risks to the pregnant woman and fetus. There is no clinical or behavioral intervention involved in the study. Pregnant women are not being specifically targeted but may participate. Excluding them will limit the generalizability of the findings as irrespective of their pregnancy, they are as likely to be affected by mental illnesses as the general adult population.

**4. Pregnancy Termination and Determination of Viability [45 CFR 46.204(H-J)]**

**A. Will the research involve termination of a pregnancy?**

No

**5. Consent of the Pregnant Woman and Father [46.204(B), 205(B), 205(C)]**

**Information Only**

RISK TO FETUS	BENEFITS				
	NONE	TO MOTHER ONLY	TO MOTHER & FETUS	TO FETUS ONLY	
MINIMAL	Consent of mother	Consent of mother	Consent of mother	Consent of mother AND father*	
GREATER THAN MINIMAL	Not allowable	Consent of mother	Consent of mother	Consent of mother AND father*	

\*Except that the father's consent need not be obtained if he is unable to consent because of unavailability, incompetence or temporary incapacity or the pregnancy

**resulted from rape or incest.**

**6. Research Involving Neonates of Uncertain Viability [45 CFR 46.205]**

**A. Will the research involve neonates of uncertain viability?**

No

**7. Research Involving Nonviable Neonates [45 CFR 46.205(c)]**

**A. Will the research involve nonviable neonates?**

No
